1.2 Synopsis

AbbVie Inc.	Protocol Number: M11-290
Name of Study Drug: Adalimumab	Phase of Development: 3
Name of Active Ingredient: Adalimumab	Date of Protocol Synopsis: 20 November 2018
Protocol Title: A Multicenter, Randomized, Double-Blind Study of the Human Anti-TNF Monoclonal Antibody Adalimumab in Pediatric Subjects with Moderate to Severe Ulcerative Colitis	
Objective: The objective of the study is to demonstrate the efficacy and safety, and to assess the pharmacokinetics of adalimumab administered subcutaneously (SC) in pediatric subjects with moderate to severe ulcerative colitis (UC).	
Investigators: Multicenter	
Study Sites: Approximately 50 sites worldwide for the main study and approximately 10 sites for the Japan sub-study.	
Study Population: Subjects with moderate-to-severe UC from the ages of 4 to 17 prior to Baseline dosing.	
Number of Subjects to be Enrolled: 93 subjects for the main study and up to approximately 9 subjects for the Japan sub-study	
Methodology: This is a Phase 3, multicenter, randomized, double-blind trial designed to evaluate the efficacy and safety of adalimumab in pediatric subjects with moderate to severe ulcerative colitis, who have failed therapy with corticosteroids and/or immunosuppressants.	

Methodology (Continued):

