- Immunosuppressant therapy may be discontinued at or after Week 12 at the investigator's discretion.

At each study visit, in addition to routine physical examination including evaluation of extra intestinal manifestations and calculation of the PMS and PUCAI, the following will be collected:

- Anthropometric evaluations at Baseline, Week 26 and Week 52/Premature Discontinuation for determination of body mass index (BMI), and "z" scores for height and weight.
- IMPACT III Quality of Life questionnaire at Baseline, Week 8, Week 26 and Week 52/Premature Discontinuation Visit will be completed for subjects 9 years or older at the Baseline study visit.
- Bone age determination by x-ray of the wrist at Screening and at Week 52/Premature Discontinuation Visit in subjects who have not completed linear growth.
- Serum for measurement of adalimumab concentrations just prior to dosing at Baseline, Week 2, Week 4, Week 8, Week 12, Week 26 Week 34 and Week 52/Premature Discontinuation Visit and at Unscheduled Visit requiring dose change.

Methodology (Continued):

Treatment of Subjects with Disease Flare During the Study (Continued):

- Serum for measurement of Anti-Adalimumab Antibodies (AAA) just prior to dosing at Baseline, Week 4, Week 8, Week 26 and Week 52/Premature Discontinuation Visit and at Unscheduled Visit requiring dose change.
- Tanner stage at Baseline, Week 26 and Week 52/Premature Discontinuation Visit.
- Endoscopy subscore at Screening and Week 52/Premature Discontinuation Visit.

Diagnosis and Main Criteria for Inclusion/Exclusion:

Main Inclusion:

1. Subjects from the ages of 4 to 17 prior to baseline dosing.
2. Subjects with a diagnosis of UC for at least 12 weeks prior to screening confirmed by endoscopy with biopsy.

A colonoscopy will be performed during the screening period unless the subject underwent a colonoscopy within 12 months prior to Screening and appropriate documentation is available (to confirm the diagnosis without evidence of dysplasia, colon cancer or infection). In this case the screening endoscopy may be either a colonoscopy or a flexible sigmoidoscopy.

If the subject underwent an endoscopy within 56 days of Baseline, and a video recording of the endoscopy is available, the video recording may be used and no additional endoscopy will be performed during the Screening period provided that the conditions noted in Section 5.3.1.1 are met and all technical requirements are fulfilled.

Note:

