Double-Blind Maintenance Doses (in Week 8 PMS Responders only):	
Body weight adjusted maintenance dose regimen
 
Blinded adalimumab Standard dosing regimen: 0.6 mg/kg (maximum dose of 40 mg) eow with matching placebo at the alternate week
 
Blinded adalimumab High dosing regimen: 0.6 mg/kg (maximum dose of 40 mg) ew
 
Subjects who were randomized to placebo (prior to Amendment 4) receive placebo ew.
 
At or after Week 12 subjects who demonstrate a disease flare may be re-randomized to receive the following blinded-treatment.
 
 • Subjects, who are randomized to standard maintenance dose, will be re-randomized to receive either adalimumab re-induction dose (2.4 mg/kg [maximum of 160 mg]) or to adalimumab (0.6 mg/kg [maximum of 40 mg]) at the visit. Afterwards, all subjects will resume to receiving the standard dose adalimumab (0.6 mg/kg [maximum of 40 mg] eow) within the original dosing schedule. • Subjects who are randomized to high maintenance dose, will be re-randomized to receive either adalimumab re-induction dose (2.4 mg/kg [maximum of 160 mg]) or to receive adalimumab (0.6 mg/kg [maximum of 40 mg]) at the visit. The following week, all subjects will resume to receiving the high dose (0.6 mg/kg [maximum of 40 mg] ew). • Subjects who were randomized to placebo prior to Amendment 4 will be re-randomized to receive either adalimumab re-induction dose (2.4 mg/kg [maximum of 160 mg]) or to receive adalimumab (0.6 mg/kg [maximum of 40 mg]) at the visit. Afterwards, all subjects will receive the standard dose (0.6 mg/kg [maximum of 40 mg] eow) within the original dosing schedule.
Open-Label Maintenance Doses:	
High dose body weight adjusted.
 
0.6 mg/kg (maximum dose of 40 mg) ew
 
If a subject continues to meet the definition of disease flare following a 4-week course of open-label adalimumab ew at the dose 0.6 mg/kg [maximum of 40 mg], they may be switched to receive adalimumab 40 mg ew (maximum dose, not weight-based).

Mode of Administration:	
Subcutaneous injection (SC)

Reference Therapy:	
NA (after Amendment 4); Placebo (prior to Amendment 4)

Dose:	
NA

Mode of Administration:	
NA (after Amendment 4); Subcutaneous injection (SC) (prior to Amendment 4)

Duration of Treatment: 52 weeks

- The subjects will visit the site at Screening, Baseline, Weeks 1, 2, 4, 8, 12, 18, 26, 34, 42, and 52/Premature Discontinuation and Unscheduled Visits.

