4. WPAI

The WPAI was developed to measure the effect of disease on productivity at work and its impact on daily activities. The questions ask about the impact of disease to the patient's caregiver within the past 7 days. Six questions asked on this questionnaire can be described briefly as follows:

Questions:

- Q1. Currently employed (working for pay)? (Yes/No)
- Q2. Hours missed from work due to PROBLEM.
- Q3. Hours missed due to other reasons.
- Q4. Hours actually worked.
- Q5. Degree PROBLEM affected productivity while working.

Q6. Degree PROBLEM affected regular activities other than job.

WPAI scores are expressed as percent impairment based on the above questions. The four main impairment measures or scores are derived as follows:

Scores:

S1. Absenteeism: Percent work time missed due to PROBLEM:

$$100 \times \left[\frac{Q2}{Q2 + Q4} \right]$$

S2. *Presenteeism*: Percent impairment while working due to PROBLEM:

$$100 \times \left\lceil \frac{Q5}{10} \right\rceil$$

S3. Percent *overall work impairment* due to PROBLEM:

$$100 \times \left[\frac{Q2}{Q2 + Q4} + \left\{ 1 - \frac{Q2}{Q2 + Q4} \right\} \times \frac{Q5}{10} \right]$$

S4. Percent *activity impairment* due to PROBLEM: $100 \times \left\lceil \frac{Q6}{10} \right\rceil$

5. Other

[figure not shown]
Body Mass Index (BMI, in kg/m^2) will be obtained as: BMI = weight (kg)/(height [m] × height [m])

"z" score for height velocity will be obtained as: (Observed height velocity [cm/yr] – mean height velocity for age and sex [cm/yr]/[SD of the mean]). NOTE: The mean and Standard Deviation (SD) will come from published table values:

The CDC Growth Charts webpage of the Center for Disease Control and Prevention with derivation details on the "z" score:

http://www.cdc.gov/growthcharts/percentile_data_files.htm, STATAGE.xls ('stature-for-age-chart', for height) to be used.

Inappropriate Tanner stage will be defined depending on age and sex as follows: girls ≥ 14 years/boys ≥ 15 of age with a Tanner stage of 1; girls ≥ 16 years/boys ≥ 18 of age with a Tanner stage < 4; girls ≥ 19 years/boys ≥ 19 of age with a Tanner stage of < 5.

7.0 Demographics, Baseline Characteristics, Medical History, and Previous/Concomitant Medications

All demographic and Baseline summaries, medical history, and prior/concomitant medications will be provided for the ITT, ITT-E, mITT, mITT-E, RR and safety population by treatment groups defined in Section 5.1, unless otherwise specified.

[figure not shown]

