10.4 Secondary Efficacy Analyses

[figure not shown]
The secondary efficacy endpoints are divided into two groups. The first group consists of ranked secondary efficacy endpoints. The second group includes all other secondary efficacy endpoints and special assessments.

The ranked secondary efficacy endpoints in hierarchical order are:

[figure not shown]
- Proportion of subjects in Mayo clinical response at Week 52 in Week 8 responders per PMS;
- Proportion of subjects who achieve mucosal healing at Week 52 as measured by Mayo endoscopy subscore (defined as ≤ 1) in Week 8 responders per PMS;
- Proportion of subjects who achieve Mayo clinical remission at Week 52 in Week 8 remitters per PMS;
- Proportion of subjects receiving systemic corticosteroids (UC related or non-UC related) at Baseline who have discontinued systemic corticosteroids prior to Week 52* and are in Mayo clinical remission at Week 52 in Week 8 responders per PMS.

Additional exploratory secondary analyses will be performed for:

[figure not shown]
- Proportion of subjects in PMS clinical remission at Week 52 in Week 8 responders per PMS;
- Proportion of subjects in PUCAI remission (defined as < 10) at Week 8;
- Proportion of subjects in PUCAI response (defined as a decrease in PUCAI
 ≥ 20 points from Baseline) at Week 8;

- Proportion of subjects in PUCAI remission (defined as < 10) at Week 52 in Week 8 responders per PMS;
- Proportion of subjects in PUCAI response (defined as a decrease in PUCAI
 ≥ 20 points from Baseline) at Week 52 in Week 8 responders per PMS;
- Proportion of subjects receiving systemic corticosteroids at Baseline who discontinue systemic corticosteroids prior to Week 52* and are in PUCAI remission at Week 52 in Week 8 responders per PMS;
- Change from Baseline in total IMPACT III Quality of Life score and subscores over time for subjects at least 9 years old at Baseline;
- Change from Baseline in WPAI scores over time;
- Change from Baseline in "z" scores for height at Week 26 and Week 52;
- Change from Baseline in BMI at Week 26 and Week 52;
- Change from Baseline in "z" scores for weight-for-age at Week 26 and Week 52;
- Proportion of subjects at appropriate Tanner stage (see Section 6.0) at Baseline, Week 26 and Week 52 (OC analysis);
- Proportion of subjects in PMS response over time;
- Proportion of subjects in PMS remission over time;
- Proportion of subjects in PUCAI response over time;
- Proportion of subjects in PUCAI remission over time;

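### Two exploratory growth outcomes are mixed with age: the Tanner proportion counts children too young for any criterion as appropriate, and BMI change is not age-standardised

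*SAP*

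**What the plan says.** SAP section 6.0 (Score Definitions, item 5, Other) defines only inappropriate Tanner stage, by three age- and sex-specific rules:

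- Rule 1: "girls ≥ 14 years/boys ≥ 15 of age with a Tanner stage of 1"
- Rule 2: "girls ≥ 16 years/boys ≥ 18 of age with a Tanner stage < 4"
- Rule 3: "girls ≥ 19 years/boys ≥ 19 of age with a Tanner stage of < 5"

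SAP 10.4 lists the endpoint as "Proportion of subjects at appropriate Tanner stage (see Section 6.0) at Baseline, Week 26 and Week 52 (OC analysis"). It neither limits the denominator to children whom a rule can reach nor says whether age at Baseline or age at the visit applies. The protocol synopsis sets eligibility as "Subjects from the ages of 4 to 17 prior to baseline dosing" and gives "Duration of Treatment: 52 weeks".

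For BMI, SAP 6.0 uses weight divided by height squared, and SAP 10.4 lists "Change from Baseline in BMI at Week 26 and Week 52". The neighbouring height and weight endpoints in the same list are z scores. All of these are exploratory. Under SAP 10.1 and 10.4 they are reported by treatment group. Neither Tanner stage nor BMI appears in the list of high-versus-standard dose tests, and neither has an external placebo rate in SAP 10.2.

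**The concern.** A rule that flags only late puberty leaves every younger child appropriate by construction. Keeping those children in the denominator pulls the proportion toward 100%, and the pull depends on the age mix of the group. A real delay among the older children would be hard to see.

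BMI has a related problem. Children grow over a year, and a raw change from Baseline does not separate that growth from a change in nutritional status.

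Protocol 3.2 says therapy for paediatric UC should not harm linear growth or maturation, so a reader will look at these tables for reassurance. With no external rate and no planned between-dose test for either outcome, the within-group result is what will be read.

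**Working it through.** The documents state no rate, sample size or power for either outcome, so there is no planned figure to reproduce.

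**Inputs.** Entry age 4 to 17, so below 18.0 (Protocol synopsis). The three Tanner rules (SAP 6.0). Week 52 window Day 331 to 399, nominal Day 365 (SAP 6.0). Incidence of UC by age in Northern France and in Poland (Protocol 3.2), used only as stand-ins because the enrolled age distribution is not given. Sex ratio 50:50, assumed.

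**Step 1: which rules can apply.** Take a child one day short of 18 at entry (17.997 years).

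- Nominal Week 52: 17.997 + 364/365.25 = 18.994.
- Last window day: 17.997 + 398/365.25 = 19.087.

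Rule 3 is therefore empty at Baseline and at nominal Week 52. To reach 19 by Day 399 a child must be at least 19 − 398/365.25 = 17.91 years at entry, which is within about 33 days of the 18th birthday, and be assessed late in the window. Rule 2 for boys (age 18 or more) is empty at Baseline and later reaches only boys aged 17 at entry.

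**Step 2: share of children old enough for Rule 1.** This is the mean of the share of girls aged 14 or more and the share of boys aged 15 or more.

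- Uniform ages: girls 4/14 = 28.6%, boys 3/14 = 21.4%, mean 25.0%.
- Northern France incidence: the weights for ages 4 to 17 sum to 0.1 + 5 × 0.3 + 5 × 1.1 + 3 × 2.5 = 14.6. Girls (1.1 + 7.5)/14.6 = 58.9%, boys 7.5/14.6 = 51.4%, mean 55.1%.

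The other mixes are worked the same way. The Week 52 column makes every child one year older, using age at visit.

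| Assumed age mix | Old enough, Baseline | Old enough, Week 52 |
|---|---|---|
| Uniform | 25.0% | 32.1% |
| Poland, incidence | 34.6% | 44.5% |
| Poland, cumulated over age | 47.4% | 57.7% |
| N. France, incidence | 55.1% | 62.7% |
| N. France, cumulated over age | 57.7% | 67.4% |

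**Step 3: dilution.** Reported inappropriate share = rate among classifiable children × share classifiable. With an assumed rate of 10%:

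- Baseline: 0.10 × 25.0% = 2.5% up to 0.10 × 57.7% = 5.8%, so 97.5% to 94.2% read as appropriate.
- Week 52: 3.2% to 6.7% inappropriate, so 96.8% to 93.3% appropriate.

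If the true rate doubled to 20%, the Baseline table would still show 95.0% to 88.5% appropriate.

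**Step 4: direction of the age effect.** With a constant 10% rate and age at visit, the appropriate share changes by −0.10 × (Week 52 share − Baseline share). This runs from −0.10 × 7.1 = −0.7 points (uniform) to −0.10 × 10.3 = −1.0 points (Poland, cumulated).

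**Step 5: BMI.** Of the three size measures in SAP 10.4, height and weight are referenced to age and BMI is not. The documents give no BMI-for-age reference values, so neither the size nor the direction of the growth component can be computed from them.

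**The case against.** The strongest defence is that both outcomes are exploratory and no decision rests on them. The trial also reports height and weight-for-age z scores and collects bone age, so a reader does not depend on Tanner stage and BMI alone. The Tanner limits may be sourced: the SAP's numbered reference is a review article on disorders of puberty. Under a definition of delay, a 10-year-old at stage 1 is rightly not delayed. All of this stands, and it limits the importance of the point. It does not remove the dilution or explain why BMI alone is left unstandardised.

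Four stronger readings are tempting, and the documents do not support them.

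- A reader might infer that most enrolled children are out of reach of the Tanner rules. For Rule 1 that is not shown: 25% to 58% are old enough at Baseline under the mixes above, and no enrolled ages are given.
- A reader might infer that the Tanner table will show a false improvement. The same rule applies at every visit, and ageing lowers the appropriate share slightly. The effect is a ceiling on the level.
- A reader might infer that Baseline and Week 52 are judged by different criteria because a boy at stage 1 changes class on his 15th birthday. That is how a single age-referenced rule works, and it arises only if age at visit is used, which the SAP leaves open.
- A reader might put a figure on the BMI drift. None is available here, and the randomised maintenance groups share any drift in expectation.

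There is also a fair objection to the obvious remedy. If the Tanner proportion is restricted to children old enough at each visit, the denominator grows with birthdays and the comparison with Baseline mixes different children. The fix must deal with that.

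**Conclusion.** The point holds as a narrow one. The Tanner proportion, as defined, dilutes pubertal delay: a 10% rate among classifiable children would read as about 2.5% to 6% at Baseline and about 3% to 7% at Week 52. Those ranges rest on the assumed 10% rate, five assumed age mixes and a 50:50 sex ratio. Two findings need no assumption about the age mix: the boys' age-18 rule cannot apply at Baseline, and the age-19 rule needs a child almost 18 at entry who is assessed late in the Week 52 window (maximum age about 19.1). Within-group BMI change mixes growth with treatment by an amount the documents cannot show. The co-primary and ranked secondary analyses are untouched. This is a cheap improvement.

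**What to change.** 1. Add change in BMI-for-age z score at Weeks 26 and 52, or substitute it for raw BMI change, using the CDC growth chart data that the SAP already cites. The SAP names only the stature file, so name the BMI reference as well.
2. Report the Tanner proportion among children old enough for a criterion (girls 14 or more, boys 15 or more). Give denominators and state whether age at Baseline or at the visit is used.
3. For the comparison with Baseline, use a fixed set, namely children old enough at Baseline, so that the same children are compared.
4. Add a shift table of Tanner stage from Baseline to Weeks 26 and 52, by sex and baseline age, for all children. It shows the stages themselves, so it is not affected by children who cross the Rule 2 ages during the study, which the fixed set alone does not solve.

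The cost is SAP wording, two extra exploratory tables and a smaller Tanner denominator. Age, sex, height, weight and Tanner stage are already collected.

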7.1 Demographic and Baseline Characteristics

Demographics and baseline disease characteristics and UC disease history values will be summarized by treatment group using descriptive statistics. *P* values will be provided to assess the comparability of the treatment groups in ITT-E and mITT-E assigned by randomization

Demographics and baseline characteristics:

• Subject demographics

- Sex (female, male)
- Age [years]
- \circ Age categories (< 13 years, \geq 13 years)
- Age categories (< 12 years, \geq 12 years)
- Race (White, Black, Asian, American Indian/Alaska Native, and Other)
- Ethnicity (Hispanic or Latino, Japanese, no ethnicity)
- o Geographic region (North America, Western Europe, Eastern Europe)
- Disease severity per Baseline Mayo score* $(\leq 9, \geq 9)$
- Prior exposure to anti-TNF* (yes, no)
- Baseline systemic corticosteroid use* (yes, no)
- Baseline immunosuppressants (IMM) use (yes, no)
- Body Weight [kg]
- o Body Weight categories ($< 40, 40 < 60, \ge 60 \text{ kg}$)
- Height [cm]
- \circ BMI [kg/m²]

- Tobacco/Nicotine Use (current user, former user, never, or unknown)
- Alcohol Use (current user, former user, never, or unknown)

[figure not shown]
*the true Baseline Mayo score and medication information from EDC to be used and a footnote to be added for cases where these values are discrepant to the values from IRT.

• PPD skin test/QuantiFERON®-TB Gold test/TB prophylaxis

- \circ Tuberculin PPD skin test (negative, positive), positive defined as ≥ 5 mm
- QuantiFERON-TB Gold test (negative, positive, indeterminate)
- Combined result of Tuberculin PPD skin test and QuantiFERON-TB Gold test
- Enrollment under TB prophylaxis (yes, no)

• Disease characteristics at Baseline

- Duration of UC
 - In months: (Baseline date date of diagnosis of UC + 1)/(365.25/12)
 - In years: (Baseline date date of diagnosis of UC + 1)/365.25
- Site of UC (Left sided UC vs. Extensive UC/pancolitis)
- Mayo Score
- Partial Mayo Score
- Endoscopy Subscore
- Rectal Bleeding Subscore
- PGA Subscore
- Stool Frequency Subscore
- Number of stools in the last 24 hours prior to baseline (i.e., last non-missing value $-1 \le Rx$ Day ≤ 1)
- PUCAI
- IMPACT III total score and subscores
- WPAI (Absenteeism, Presenteeism, Work Impairment, Activity Impairment)

o hs-CRP [mg/L]

7.2 Medical History

Medical history data will be summarized and presented using System Organ Class (SOC) and Preferred Terms (PT) according to the Medical Dictionary for Regulatory Activities (MedDRA) dictionary. The SOCs will be presented in alphabetical order and the PTs will be presented in alphabetical order within each SOC. The number and percentage of subjects with a particular PT will be summarized. Subjects reporting more than one PTs within a SOC will be counted only once for that SOC.

[figure not shown]
7.3 Prior Treatment and Concomitant Medications

Prior medications are those medications taken prior to the first dose of induction study drug. This includes medications with a start date before the first study drug administration date, regardless of the end date of these medications. Medications taken on the day of the first dose of study drug are not counted as prior medications.

In cases where incomplete or missing medication dates are collected, a conservative approach will be taken such that if a medication could have been a prior medication, it will be counted as a prior medication.

Baseline medications are those medications that subjects were on at the time of the first dose of induction study drug. This includes medications that started prior to the first dose of study drug and continued after the first dose of study drug or ended at the time of the first dose of study drug, as well as, medications that began on the day of the first dose of study drug.

Concomitant medications during respective study phase (see Table 4 below) are those medications, other than study drug, taken after the first dose of study drug on/after start of the respective study phase and within (max.*) 14 days of the last dose of study drug in the respective study phase. This includes medications with a start date between first study drug administration and last study drug administration + (max.*) 14 days, as well as,

medications with a start date prior to first dose of study drug and which are ongoing after first dose of study drug. Medications taken on the day of the first dose of study drug are counted as concomitant medications.

*Medications which started after the first dose of study drug in the maintenance period should not be considered concomitant in the induction period, even if they occurred within 14 days of the last dose of study drug in the induction period. Medications which started after the first dose of study drug in Study M10-870, if applicable, should not be considered concomitant in the maintenance period/whole study period, even if they occurred within 14 days of the last dose of study drug in the maintenance period.

In the situation where an incomplete or missing medication date is collected (start or end date), a conservative approach will be taken such that if a medication could have been a concomitant medication, it will be counted as a concomitant medication.

Note that a medication can be considered a prior, a baseline and a concomitant medication if it started prior to the first dose of study drug and continued after the first dose of study drug.

The medications will be coded by WHO DRUG dictionary. The number and percentage of subjects who had taken medications will be summarized by generic drug name for all medications as well as for those flagged as UC-related medications. No statistical tests will be performed.

The number and percentage of subjects with prior as well as baseline anti-diarrheal therapy, NSAIDs, biologic DMARDs, synthetic DMARDs, IBD related antibiotics, anti-TNF biologics, non-anti-TNF biologics, systemic corticosteroids and among those the oral corticosteroids, IMM and aminosalicylates will be summarized. In addition, four groups of baseline IMM and/or systemic corticosteroids use (IMM with systemic corticosteroids, IMM without systemic corticosteroids, systemic corticosteroids without IMM, and neither IMM nor systemic corticosteroids) will be tabulated.

[figure not shown]

Table 4. Overview of Analyses for Prior, Baseline, and Concomitant Medications

	ITT(-E)	mITT(-E)	RR	Safety
Prior Medications	X			X
Baseline Medications	X			X
Concomitant Medications				
Induction (Week 0 – Week 8*)	X			
Maintenance (Week 8 – Week 52)		X	X	
Whole Study (Week 0 – Week 52)				X

^{*} The induction period does not include the dose received at Week 8.

